## **Study Design**

This is a prospective randomized controlled single site trial.

## 2. BACKGROUND

Endoscopic ultrasound is a common procedure performed in ambulatory surgical centers in the U.S. Most patients undergoing endoscopy require sedation to have an acceptable experience. In endoscopic ultrasound (EUS), sedation is a necessity because the ability to interpret images and perform therapeutic or diagnostic procedures are dependent on the subjects cooperation. Reliable imaging cannot be obtained if the patient is not cooperative. Propofol is a commonly used sedative that has been used in several studies for endoscopic procedures and is associated with low complication rates in healthy patients (ie: ASA I and II). However, recent prospective studies have shown that hypoxemia frequently occurs during endoscopic procedures in patients with a BMI >  $30 \text{kg/m}^2$  or have a history of OSA  and the mortality rate for sedation in the endoscopy suite is significantly higher than that of the comparable cases performed in operating room. Although the cause of the high mortality in GI suite has yet to be determined, it seems to be related to hypoxia and/or hypercarbia due to respiratory depression and upper airway obstruction from sedation.

Continuous positive airway pressure (CPAP), applied nasally or via facemask, has been shown to be more effective at minimizing hypoxia than other devices under sedation or general anesthesia. However, it requires a special mask and CPAP machine with high-fresh gas flows which may not be routinely equipped in GI endoscopy suites due to space and cost constraints. Therefore, a simplified CPAP system could be a surrogate for a conventional CPAP machine for procedures requiring sedation or general anesthesia with spontaneous breathing via a natural airway. Recently, a simple, novel CPAP device was developed, which includes a sealed nasal mask and disposable, flow-inflating hyperinflation bag (SuperNO2VA Et™ Satellite Set, Revolutionary Medical Devices, USA). A small pilot study by Ghebremichael, et al. demonstrated safety and efficacy with the use of the SuperNO2VA Et™ device for nasal mask ventilation (NMV) in anesthetized and paralyzed patients. The objective of our study is to compare oxygenation in spontaneously ventilating obese patients or those with diagnosed or undiagnosed OSA undergoing endoscopic ultrasound under propofol based sedation in an ambulatory surgical center between the SuperNO2VA Et™ nasal positive airway pressure (PAP) device and routine care with nasal cannula for O2 supply. In a simulated patient setup, the SuperNO2VA ET CO2Nasal mask are accurate for measurements of end tidal carbon dioxide (etCO2).

### 3. DISCUSSION OF SUBJECT POPULATION

## 3.1. Subject Characteristics

The study population for this investigation is all adults who have a BMI > 35 kg/m^2 or documented OSA scheduled to receive Propofol based sedation for Endoscopic Ultrasound.

### 3.2. Inclusion and Exclusion Criteria

#### a) Inclusion Criteria:

- 1. Age 18 years of age or older
- 2. Patients undergoing upper endoscopic ultrasound
- 3. American Society of Anesthesiology (ASA) Physical Status I-III
- 4. BMI  $\geq$  35 kg/m^2 or documented Obstructive Sleep Apnea
- 5. Has provided written informed consent

#### b) Exclusion Criteria:

- 1. Inpatient status
- 2. Active Congestive Heart Failure Exacerbation
- 3. Untreated ischemic heart disease
- 4. Acute exacerbation of respiratory disorders, including COPD and asthma
- 5. Emergent procedures
- 6. Pregnancy
- 7. Previous enrollment in this study
- 8. Inability to provide informed consent
- 9. Additional medical testing planned for the same day
- 10. History of allergic reaction to Propofol
- 11. Tracheostomy
- 12. Supra-glottic or sub-glottic tumor
- 13. Gastrointestinal tract obstruction or delayed transit (including delayed gastric emptying, gastric bezoar, achalasia, toxic megacolon).

#### 3.3. Discussion of Subject Population:

Patients with either a BMI  $\geq$ 35 kg/m^2 or a documented Obstructive Sleep Apnea scheduled for Endoscopic Ultrasound with Propofol sedation at are increased risk for severe hypoxemia intra-operatively and post-operatively due to Propofol's relaxant effect on muscle of the upper airway. In addition patients with OSA usually fall into three scenarios. Those that are diagnosed with OSA and are using their CPAP, those that are diagnosed with OSA but do not use CPAP, and the undiagnosed OSA patient. Therefore, more patients

than not are at risk for cardiopulmonary morbidity intra-operatively and immediately after Propofol based sedation.

## 4. SUBJECT IDENTIFICATION, RECRUITMENT AND CONSENT

### 4.1. Method Of Subject Identification And Recruitment

Subject consenting will take place at the GLES immediately prior to the procedure by key research personnel such as PI, Co-PIs, and/or study coordinators. Subject initials and/or study identification number will refer to the subjects.

#### 4.2. Consent Process

Subjects deemed eligible to participate in the study will be explained in detail the purpose, nature and procedures of the study, as well as the potential risks, benefits and alternatives. They will be given a consent form to read and if they so choose, to discuss with friends, family, and other clinicians. They will be invited to ask questions and, after all questions are answered to their satisfaction, invited to sign the consent form. The Principal Investigator (with proper delegation of authority) will participate in the consenting process to ensure the subject has full understanding of the procedure and risks. No study-specific procedure will be performed before the consent form is signed.

Subject participation in this investigation is voluntary. Written informed consent is required from all subjects prior to the subject's participation in the investigation. Also, an obtained permission of the faculty anesthesiologist, in charge of the patient's anesthesia care, must also be granted for subject participation. If the subject is illiterate or unable to adequately read the informed consent form, a witness' signature and a cross mark or a fingerprint of the subject is required. In accordance with FDA regulation 21 CFR Part 50, informed Consent shall be obtained prior to any study procedure. The original of the signed consent will be retained at the investigational site. A signed copy of the consent will be given to the subject. While not anticipated, Sponsor will report any failure to obtain subject consent to the IRB within 5 days of learning of such an event, as required by regulation.

Prior to participating in this investigation, the site will be required to have an IRB-approved Informed Consent Document. Any modifications to the consent must be approved by Sponsor and by the IRB of record. The Principal Investigator at each study site is responsible for obtaining and maintaining the approved informed consent and forwarding an IRB-stamped copy to Sponsor.

#### 4.3. Costs to the Subject

None

- 4.4. Payment for Participation None
- 4.5. Return of Individual Research Results Not Applicable.

#### 5. METHODS AND STUDY PROCEDURES

5.1 Instruments

The SuperNO2VA™EtCO2 (Nasal Oxygenating Ventilating Apparatus) mask is indicated to deliver gas, create a seal, and provide positive pressure while placed over a patient's nose and connected to either an anesthesia circuit or hyperinflation bag during respiratory, anesthesia, and resuscitation procedures. The SuperNO2VA™EtCO2 mask is also intended to facilitate simultaneous oxygenation and ventilation during intubation, as the mask covers only the patient's nose, leaving the clinician with an unobstructed view of the airway.

### 5.2 Methods:

This study involves the oxygenation, continuous positive airway pressure, and ventilation of a subject via nasal mask and oxygenation via a closed facemask. The interventions directly related to this study are that of supplement oxygen, bag-mask ventilation, and continuous nasal CPAP intra-operatively and in the Post Anesthesia Care Unit.

Patients will be randomized in groups of ten to one of two groups using a random number table. Group A: Standard care with a nasal cannula. Group B: SuperNO2VA™EtCO2.

For each anesthetic case, a preoperative history and physical and intraoperative record will be documented (table 1).

Table 1: General Patient characteristics	
Age (years)	
Gender (M/F)	
Height (cm)	
Weight (kg)	
BMI (kg/m  )	
ASA classification (I-III)	
Diagnosed OSA on home CPAP	
Diagnosed OSA not on home CPAP	
STOP-BANG Score	
Patient Co-morbidities*	

\*Co-morbidities include any history of: hypertension, diabetes, coronary disease, valvular disease, arrhythmia, cerebrovascular disease, active cancer, tobacco use, pulmonary disease, renal disease, liver disease.

Once in the endoscopy suite, the patients will have continuous monitoring of heart rate, end tidal CO2 (EtCO2), O2 saturation, and every 2-minute BP monitoring. Patients randomized to group A, the anesthesia provider will supply oxygen via nasal cannula at 10LPM. Patients randomized to group B, the anesthesia provider will attach the SuperNO2VAM EtCO2's circuit port to the hyperinflation bag with the oxygen flow rate to 10 L/min, and the APL valve completely closed. Initial dosing bolus 0.5-1.0 mg/kg actual body weight of Propofol will be administered for sedation and MOAA/S scores will be assessed. Nursing or the research assistant will then record the patient's MOAA/S score. If the patient's MOAA/S score of <4 reached. Once a MOAA/S score of <4 is reached the endoscopist will perform endoscopic intubation and the goal will be to maintain a MOAA/S score of <4 until the procedure is over. If the patient's MOAA/S score  $\geq 4$ , additional 10 – 40mg bolus of propofol will be administered every 30–90 seconds until the

Protocol #: IU IRB# 1810997768 Date: 31AUG21 Page 9 of 17

MOAA/S is <4. The measurements that will be made are the following: the incidence, severity, and time of oxygen desaturation, number of airway maneuvers performed, duration of airway maneuvers, reason for performing the airway maneuver, the onset time of administration of sedation, the duration of the procedure, the total dosage of the medication, vital signs - blood pressure, heart rate, and oxygen saturation, the time to full recovery, and patient cooperation. Nursing or the research assistant will document their patient's depth of sedation, cooperation with procedure, and safety. Patients will recover in the endoscopy suite. The patients will have continuous monitoring of heart rate, end tidal CO2 (EtCO2), O2 saturation, and every 5-minute BP monitoring and MOAAS Score. The time to discharge will be obtained for each patient. Patients will also complete a satisfaction and pain questionnaire before they are discharged. Patients will also be asked to complete another questionnaire within 48 hours concerning their satisfaction and their subjective degree of impairment due to the sedation either with a paper form and self-addressed envelope or electronically sent via e mail. If the patients do not complete their questionnaire, someone will contact them by telephone to collect the data. A statistician using student T-test, Fishers exact test, and other statistical methods they deem appropriate will analyze the collected data.

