Follow-up Visits	Patient will complete a mail-in survey after 48 hours.
End of Study Visit	N/A
Brief Analysis Plan	Based on the literature the incidence of hypoxemia (ie: oxygen saturation < 90% for > 15 seconds) in using supplemental oxygen with nasal cannula is as high 43%. (Patel et. al.) Thus we expect the complication rate of hypoxemia in the SuperNO 2 VA™EtCO2 group to be 13%, we need 62 patients per group (112 patients in total) to detect this expected difference with 80% power at 0.05 two-sided level of significance. To adjust for 10% missing rate, we need approximately 124 patients in total.

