# **Endpoints of Interest**

- 1. Compare the amount of propofol administered during induction and total dose administered for procedure
- 2. Compare Modified Observer's Assessment of Alertness/Sedation Scale (MOAAS) scores immediately prior to endoscopic intubation and during the procedure

Protocol #: IU IRB# 1810997768 Date: 31AUG21 Page 5 of 17

- 3. Compare the length of time from induction to endoscopic insertion
- 4. Compare the incidence and duration of procedural interruptions (ie: number of times and length of time the endoscope is removed from the patient)
- 5. Compare the incidence, duration, and reason for airway maneuvers
- 6. Compare the length of time for the procedure (ie: length of time from procedure start to procedure end)
- 7. Compare recovery times
- 8. Compare patient satisfaction scores (visual analog scale (VAS)) immediately after procedure
- 9. Compare patient satisfaction scores 48 hours later
- 10. Compare patient tolerance to SuperNO2VA EtCO2 compared to control (ie: nasal cannula at 10LPM)
- 11. Compare endoscopist satisfaction scores for
- 12. Compare anesthesiologists satisfaction scores
- 13. Compare the incidence of cardiac complications

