### **10. SAMPLE SIZE DETERMINATION AND DATA ANALYSIS**

### 10.1. Sample Size Determination

Power analyses were performed for the three primary objectives, using a power level of 0.80 and an alpha

Protocol #: IU IRB# 1810997768 Date: 31AUG21 Page 13 of 17

level of 0.05. Based on the literature the incidence of hypoxemia (ie: oxygen saturation < 90% for > 15 seconds) in using supplemental oxygen with nasal cannula is as high 43%. (Patel et. al.) Thus we expect the complication rate of hypoxemia in the SuperNO2VA EtM group to be 13%, we need 62 patients per group (124 patients in total). This sample size will allow us to detect this expected difference with 80% power at 0.05 two sided level of significance. To adjust for 10% missing rate, we need approximately 124 patients in total.

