#### **10.3.** Planned Statistical Analysis

Although randomization into treatment groups should minimize differences between the groups, basic bivariate analyses will be performed to determine if there are any clinical or demographic differences, using the data collected in table 1. Logistic regression models will be performed to determine if there are significant differences between the groups for both incidence and severity. Student's t-tests will be performed to determine if there is a significant difference between groups for duration, with Wilcoxon non-parametric tests being performed if the data are non-linear. If significant differences in clinical or demographics characteristics were found, multivariable models will be performed to adjust for these possible confounding variables using logistic regression and ANCOVA models (with GEE models being used to model non-linear data with the appropriate exponential family distribution). All analytic assumptions will be verified and all analyses performed with SAS v9.4, SAS Institute, Cary, NC), analyzing the data as both per-protocol and intention-to-treat.

A Data Safety and Monitoring Board (DSMB) will be convened once half the necessary study population has been enrolled, to discuss the current status of primary endpoints and adverse events, all of which will be tabulated throughout the study. If effect sizes are larger than originally planned and there is a statistically significant decrease in the primary event at this halfway mark, the study will end at this time.

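### Planned EUS type is not recorded and no covariate is prespecified for procedure time or total propofol, so these two secondary comparisons forgo some precision

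*Protocol*

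**What the plan says.** **Data items.** Protocol 5.2 states: "For each anesthetic case, a preoperative history and physical and intraoperative record will be documented (table 1"). Table 1 lists age, gender, height, weight, BMI, ASA class, diagnosed OSA with or without home CPAP, STOP-BANG and co-morbidities. The measurements listed later in 5.2 include procedure duration and total drug dose, but not the kind of EUS planned or done. The baseline data named in Protocol 10.2 and SAP 1.2 are age, gender, height, weight and BMI, collected after group assignment.

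**Case mix.** Inclusion criterion 2 (Protocol 3.2) admits any upper EUS. The Background acknowledges that the ability to "perform therapeutic or diagnostic procedures are dependent on the subjects cooperation".

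**Outcomes.** Endpoints of Interest 1 is propofol dose at induction and in total. Endpoint 6 is "Compare the length of time for the procedure (ie: length of time from procedure start to procedure end").

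**Analysis.** Protocol 10.3 and SAP 1.3 say that "basic bivariate analyses will be performed to determine if there are any clinical or demographic differences, using the data collected in table 1". Multivariable models follow only if that screen finds a significant difference. The analyses named there cover the incidence, severity and duration of desaturation. Neither section names a model for procedure time or propofol dose. Protocol 5.2 leaves other methods to the statistician.

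**The concern.** A purely diagnostic examination and one with sampling or therapy may well differ in length. Protocol 5.2 keeps the patient at the target sedation level until the procedure ends, so total propofol can be expected to rise with length. If type matters, it adds variance to both outcomes in both arms. A covariate fixed before assignment would remove that part.

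As written, the plan does not do this. Type is not in Table 1, so the balance screen cannot show it and the adjusted models cannot take it up. Adding it to Table 1 alone would change little, because adjustment waits for a significant imbalance, whereas the precision gain comes from adjusting whether or not there is one. At stake are wider intervals than necessary for two of the 13 secondary endpoints.

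**Working it through.** **Plan figure used.** Only the arm size of 62 is taken from the plan. For 43% vs 13% at two-sided 0.05 and 80% power, the pooled formula gives 34 per group, or 38 after 10% missing, so the stated 62 does not reproduce. The Summary Table also puts the total at 112 where Protocol 10.1 has 124. That is a separate matter. The percentage reductions below do not depend on the arm size.

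**Assumed inputs** (none is in the documents): share of procedures with sampling or therapy, m = 0.2 to 0.5; extra time for these, d = 10 to 20 min; within-type standard deviation, s = 12 to 15 min.

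**Variance explained:** R² = m(1−m)d² / [m(1−m)d² + s²].

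- Low end (m = 0.2, d = 10, s = 15): 16 / (16 + 225) = 0.07.
- High end (m = 0.5, d = 20, s = 12): 100 / (100 + 144) = 0.41.

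**Cut in standard error:** 1 − √(1 − R²).

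- Low end: 1 − √(225/241) = 3%.
- High end: 1 − √(144/244) = 23%.

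**Equivalent extra patients for this outcome:** 1/(1 − R²) − 1.

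- Low end: 16/225 = 7%.
- High end: 100/144 = 69%.

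**Detectable difference** at 62 per arm, 80% power, two-sided 0.05: (1.96 + 0.84) × √(2/62) = 0.503 SD unadjusted. Multiplied by √(1 − R²), this becomes 0.477 SD at R² = 0.10, 0.450 at 0.20 and 0.390 at 0.40. Power for a true 0.5 SD difference rises from 79.5% to 83.5%, 87.5% and 94.9%.

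**Is chance imbalance an additional hazard?** Take m = 0.5, d = 15, s = 12.

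- Shift from chance imbalance, SD: 15 × √(2 × 0.25/62) = 1.35 min.
- Unadjusted standard error: √[2 × (56.25 + 144)/62] = 2.54 min.
- Adjusted standard error: √(2 × 144/62) = 2.16 min.

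The squares add up: 2.16² + 1.35² ≈ 2.54². The imbalance term is already inside the unadjusted standard error. With s = 15 the unadjusted figure is √[2 × (56.25 + 225)/62] = 3.01 min, and the same holds.

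**Does desaturation incidence gain?** It is analysed by logistic regression, which has no residual variance to shrink. At 43% vs 13% with 62 per arm, the large-sample standard error of the log odds ratio is √[1/(62 × 0.43 × 0.57) + 1/(62 × 0.13 × 0.87)] = 0.456. I added a two-level type with share 20-50% and odds ratio 1.5-3 (assumed), using the expected information matrix. The standard error rises to between 0.458 and 0.472, so the interval does not narrow.

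Nothing comparable was computed for total propofol.

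**The case against.** The strongest reply is that this is one of many possible covariates, for two unranked secondary endpoints, with a benefit resting wholly on assumed inputs. The assumed range of 7-69% more patients runs from negligible to large. Inpatients and emergent procedures are excluded, and nothing shows how mixed the remaining cases are. If sampling is decided on the images seen, planned type will be a noisy covariate. All of this stands. It limits the weight of the point but does not remove the omission.

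A reader might infer more than the documents support:

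- **That type cannot be adjusted for at all.** An intraoperative record is kept and its fields are not fully listed. The investigator also holds a key linking study number to medical record number (Protocol 9). The scheduled procedure may be retrievable, and Protocol 5.2 allows other methods. What is missing is prespecification.
- **That chance imbalance could pass for a device effect, so the comparison is biased.** Randomization protects against systematic bias, and the unadjusted interval already covers chance imbalance.
- **That the primary comparison also loses precision.** The logistic check shows no interval gain.
- **That type is a main driver of these outcomes, or always known at scheduling.** Both are clinical assumptions. The Background sentence is general and does not describe this trial's patients.

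**Conclusion.** The point holds as a matter of precision on two secondary outcomes. Planned EUS type is not a listed data item, and the plan adjusts only for Table 1 variables with a significant baseline difference, so it provides no adjustment for type in procedure time or total propofol. The unadjusted comparisons are valid without it.

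For procedure time, the forgone gain is about 3-23% of the standard error, if planned type explains 7-41% of the variance. Those shares rest on assumed values for case mix, time difference and spread. For total propofol the direction is plausible but the size is unknown. Neither the analysis of desaturation incidence nor the sample size depends on this. It is an optional improvement, worth making because it costs so little.

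**What to change.** 1. Add one field to Table 1: planned EUS type (diagnostic only / with sampling or therapy). Enter it from the schedule before assignment. This timing must be stated, because Protocol 10.2 and SAP 1.2 collect baseline data after assignment.
2. In Protocol 10.3 and SAP 1.3, specify models for procedure time and total propofol, since none is named now. Use ANCOVA-type linear models, on a transformed scale if the data are skewed, with arm and planned type as fixed terms. Include type whether or not it differs at baseline.
3. Use planned type, not performed type. What is finally done through the scope could be affected by the assigned device.

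**Cost:** one extra CRF field and a sentence or two in the SAP, with no extra patients or procedures. The gain shrinks if planned type often changes or is undecided at scheduling. That weakens the covariate but adds no bias, because it is fixed before assignment.

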### 10.2. Randomization

A random number generator program will be used to assign sequential qualified study cases to control group (N = 62) or SuperNO2VATMEtCO2 group (N = 62) before collection of additional demographic information and before anesthetic and surgical care. After study group assignment, baseline data will be collected, including age, gender, height, weight, and BMI.

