1.3. Planned Statistical Analysis

Although randomization into treatment groups should minimize differences between the groups, basic bivariate analyses will be performed to determine if there are any clinical or demographic differences, using the data collected in table 1. Logistic regression models will be performed to determine if there are significant differences between the groups for both incidence and severity. Student's t-tests will be performed to determine if there is a significant difference between groups for duration, with Wilcoxon non-parametric tests being performed if the data are non-linear. If significant differences in clinical or demographics characteristics were found, multivariable models will be performed to adjust for these possible confounding variables using logistic regression and ANCOVA models (with GEE models being used to model non-linear data with the appropriate exponential family distribution). All analytic assumptions will be verified and all analyses performed with SAS v9.4, SAS Institute, Cary, NC), analyzing the data as both per-protocol and intention-to-treat.

A Data Safety and Monitoring Board (DSMB) will be convened once half the necessary study population has been enrolled, to discuss the current status of primary endpoints and adverse events, all of which will be tabulated throughout the study. If effect sizes are larger than originally planned and there is a statistically significant decrease in the primary event at this halfway mark, the study will end at this time.

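### SpO2 is monitored in the suite, but no pre-device reading is defined or pre-specified as a covariate for desaturation; adding one is a cheap, minor improvement

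*Protocol*

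**What the plan says.** **Measurement.** Protocol section 5.2 says: "Once in the endoscopy suite, the patients will have continuous monitoring of heart rate, end tidal CO2 (EtCO2), O2 saturation". This comes before the text on oxygen delivery and propofol. The same section lists among the study measurements "vital signs - blood pressure, heart rate, and oxygen saturation", with no time point. No baseline SpO2 is defined anywhere. By contrast, section 5.3 defines cardiac complications as changes from baseline in blood pressure and heart rate.

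**Baseline variables.** Table 1 in section 5.2 holds age, gender, height, weight, BMI, ASA class, OSA with or without home CPAP, STOP-BANG and co-morbidities. It has no SpO2 field. Protocol section 10.2 (and SAP 1.2) says "baseline data will be collected, including age, gender, height, weight, and BMI", again without SpO2, although the list is not closed.

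**Adjustment.** Protocol section 10.3 plans that "basic bivariate analyses will be performed to determine if there are any clinical or demographic differences, using the data collected in table 1"; SAP 1.3 has the same text. Then: "If significant differences in clinical or demographics characteristics were found, multivariable models will be performed to adjust for these possible confounding variables". Incidence and severity are analysed by logistic regression, and duration by t-test or Wilcoxon test. Section 5.2 separately leaves room for the statistician, in that "other statistical methods they deem appropriate will analyze the collected data".

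**The concern.** The incidence, duration and severity of desaturation all derive from SpO2 falling to a fixed level near 90%. Eligibility sets no minimum SpO2. Only acute exacerbations of respiratory disorders are excluded, and pulmonary disease is an expected co-morbidity in Table 1, so patients may start at different distances from that level. Starting SpO2 is therefore a natural candidate covariate.

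As written, it has no defined reading and no place in the baseline table, and it is not named in any model. A chance imbalance in it would not show directly in Table 1. Using it later under the general allowance for other methods would be a post hoc choice. At stake is some power for the primary comparison, and the chance to fix the adjustment before results are known.

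**Working it through.** **Inputs from the documents.** Control rate 43%, device rate 13%, two-sided alpha 0.05, 80% power, 10% missing, 124 patients randomised 1:1 (Protocol 10.1 and 10.2, SAP 1.1 and 1.2). The Summary Table gives 112 before inflation, which is 56 per group.

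**Input assumed.** Neither document gives the prognostic strength of starting SpO2. I take an odds ratio (OR) for desaturation of 1.0 to 3.0 per SD of starting SpO2.

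**Step 1: the plan's own sample size.** With pooled variance under the null,

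n = [1.96·√(2·p̄(1−p̄)) + z·√(p₁(1−p₁)+p₂(1−p₂))]² / (p₁−p₂)², with p̄ = 0.28.

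- 80% power: [1.96·0.635 + 0.8416·0.5985]² / 0.09 = 34 per group (41 with continuity correction).
- 95% power: [1.96·0.635 + 1.645·0.5985]² / 0.09 = 56 per group.
- Inflation: 112/0.9 = 124.4, as planned.

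The stated 80% does not reproduce. At 56 per group, power for 43% versus 13% is about 95%. That is a separate matter, but it leaves little room for a covariate to add power.

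**Step 2: power with and without the covariate.** 4,000 simulated trials per setting, 56 per group, with a standard-normal baseline covariate. Logistic regression was fitted on group alone and on group plus covariate, with a two-sided Wald test at 1.96. Marginal event rates were held at the values shown.

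| OR per SD | 43% vs 13%: unadjusted → adjusted | Gain (points) | 43% vs 20% (assumed): unadjusted → adjusted | Gain (points) |
|---|---|---|---|---|
| 1.0 | 95.5% → 95.7% | 0.2 | 75.3% → 75.1% | −0.2 |
| 1.5 | 95.5% → 96.0% | 0.5 | 73.1% → 74.7% | 1.6 |
| 2.0 | 94.6% → 96.4% | 1.8 | 74.5% → 78.3% | 3.8 |
| 3.0 | 95.7% → 98.3% | 2.6 | 75.2% → 82.8% | 7.6 |

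The unadjusted figures differ between rows only by simulation error; near 75%, one SE is √(0.75·0.25/4000) = 0.7 points.

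**Step 3: where the gain comes from.** At 43% versus 13%, the median SE of the log odds ratio is 0.485 unadjusted. Adjusted, it is 0.490, 0.498, 0.520 and 0.562 for OR 1.0, 1.5, 2.0 and 3.0 per SD. The SE rises, but the conditional log odds ratio moves further from zero. At OR 3 per SD it goes from −1.656 to −2.018, so the ratio of estimate to SE goes from 1.656/0.485 = 3.41 to 2.018/0.562 = 3.59. On the risk-difference scale, the SD of the standardised estimate changes by +1%, −1%, −4% and −8% over the same range.

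**The case against.** A reader might infer that the SpO2 outcomes cannot be adjusted for starting saturation at all. The documents do not support that. Saturation is recorded, the baseline list in section 10.2 is open-ended, and section 5.2 allows other methods. The plan omits the adjustment but does not bar it.

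A reader might also infer that every primary comparison loses precision. For the planned logistic models, the SE of the log odds ratio rises with adjustment, and what is gained is power. The linear-model saving (an SE factor of 0.995 to 0.87 for correlations of 0.1 to 0.5) would need severity to be a continuous measure such as lowest SpO2. The documents do not define it so, and assign it to logistic regression. Nor is starting SpO2 a baseline value of the outcome in the usual sense: the outcome is threshold episodes, and starting SpO2 is a prognostic covariate for them.

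Three further objections have weight:

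- Prognostic strength is assumed, and a weak covariate gains nothing.
- Table 1 already holds related variables (pulmonary disease, tobacco use, BMI, OSA and CPAP status, STOP-BANG, ASA class), and the simulation does not estimate what SpO2 adds beyond them. However, those variables enter a model only after a significant imbalance, so the default comparison is the unadjusted one simulated here.
- That a pre-device reading exists is inferred from the order of the text in section 5.2; none is required. A reading taken on the assigned device is post-treatment and cannot serve as baseline.

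What remains is that a likely prognostic covariate is neither defined nor pre-specified.

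**Conclusion.** The point holds as a minor, cheap improvement and not as an error. The unadjusted randomised comparison is valid. At the planned 43% versus 13% with 56 per group, pre-specified adjustment is worth about 0 to 3 points of power on top of about 95-96%. If the true effect is smaller, for example 43% versus 20%, it is worth about 0 to 8 points, and the upper end needs an odds ratio of 3 per SD. The smaller effect deserves a look because section 10.1 presents 43% as an upper-end control rate and cites no source for the 13%. Both the smaller effect and the prognostic range are assumptions.

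Adding SpO2 to Table 1 alone would do little: under the present rule it would enter a model only when the groups happened to differ significantly.

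**What to change.** 1. Add one field to Table 1: SpO2 on arrival, before the assigned oxygen device is applied and before the first propofol dose.
2. In Protocol 10.3 and SAP 1.3, name that value as a fixed covariate in the logistic models for incidence and severity, whatever the baseline significance tests show.
3. Report the unadjusted result alongside, and state in advance which of the two is primary. The adjusted odds ratio is conditional on SpO2 and is expected to lie further from 1 than the unadjusted one; that difference alone is not evidence of confounding.
4. State that readings taken on the assigned device are not to be used as baseline, and how a missing value will be handled.

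The cost is one data field from a monitor already in use and a few lines in the SAP. For patients already enrolled, the value may be missing or available only on oxygen. The change should be made before outcomes are examined by group, including at the planned interim analysis at 62 randomised patients.
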